11.1.5 Relationship to Investigational Medicinal Product

The relationship of an AE to the administration of IMP (unrelated, probable or definite) is a clinical decision based on all available information at the time of the completion of the eCRF.

IMP relationship will be evaluated according to the following definitions:

Unrelated: includes the existence of a clear alternative explanation (e.g., mechanical bleeding at surgical site) or non-plausibility (e.g., the patient is struck by an automobile, at least where there is no indication that the IMP caused disorientation that may have led to the event; cancer developing a few days after IMP administration).

Probable: The AE, including clinical laboratory abnormality, follows a reasonable sequence from the time of IMP administration, follows a known response pattern of the IMP class, is unlikely to be attributed to the patient's clinical state, and is confirmed by improvement on stopping the IMP (de-challenge).

Definite: The AE, including clinical laboratory abnormality, follows a plausible sequence from the time of IMP (or placebo) administration; follows a known or expected response pattern to the IMP class; cannot be explained by disease or it disappears or decreases on cessation or reduction in IMP dose; and/or it reappears or worsens when the IMP is re-administered.

11.1.6 Severity

The Investigator will determine the intensity of each AE using the following terms and definitions:

Mild: An AE that was usually transient required no intervention or special treatment and did not interfere with usual/normal activities.

Moderate: An AE that interfered with usual/normal activities but was ameliorated by therapeutic measures.

Severe: An AE that was intense or debilitating and which interfered with usual/normal activities. Recovery was usually aided by therapeutic measures. Discontinuation of IMP might have been required.

11.2 Reporting of Adverse Events

All AEs that occur between randomization through Day 28 visit will be reported. AEs that start prior to study drug administration will also be captured. Worsening signs and symptoms of the underlying disease will be reported as AEs.

The course of each event should be followed until resolution. All unresolved AEs should be followed-up by the Investigator until the events are resolved, or the AE is stabilized and otherwise explained.

AEs should be recorded according to findings and abnormalities detected by the Investigator. Specific capturing of potential secondary infections will take place. In addition, patients should report AEs voluntarily and in response to general, non-directed questioning. For each AE reported by the patient, or observed by the Investigator, the Investigator should obtain all the information required to complete the AE page of the eCRF, in accordance with the guidelines that accompany it.

Atox Bio or designee assumes responsibility for appropriate reporting of SAEs to the regulatory authorities. Atox Bio or designee will also report to the Investigators all SAEs that are unexpected and associated with the use of the drug.

The Investigator must report these events to the appropriate IRB/IEC in accordance with local regulations.

11.3 Reporting of Serious Adverse Events

All SAEs occurring with any patient participating in this clinical study must be recorded. All deaths and SAEs must be reported within 24 hours of becoming aware of the event to the Sponsor or designee. All SAEs beginning within 28 calendar days after the last exposure to IMP must be recorded.

11.3.1 Initial Report

Once an Investigator becomes aware that a SAE has occurred in a study subject, the Investigator (or designate) must complete the information in the SAE eCRF pages WITHIN 24 HOURS. The SAE eCRF pages will always be completed as thoroughly as possible with all available details of the event. Even if the Investigator does not have all information regarding a SAE, the SAE eCRF pages should still be completed within 24 hours. The report should contain, at a minimum, the following information:

- Subject identifiers (i.e., subject number)
- Suspected medicinal product (or if related to IMP, note “Reltecimod/Placebo”)
- Adverse event term (must be listed as serious)
- Contact information for person reporting event

Once additional relevant information is received, the SAE eCRF pages should be updated WITHIN 24 HOURS.

The medical monitor is available on a 24-hour basis if clinical personnel wish to discuss any safety related events.

11.3.1.1 Electronic SAE Reporting System Back-up

If the electronic SAE reporting system does not work, the Investigator (or designate) must complete, then date and sign a SAE Report Form. The site should scan the document and email it to the medical monitor at [contact] and [contact] within 24 hours.

This back-up system should only be used if the electronic SAE reporting system is not working and NOT if the system is slow. As soon as the electronic SAE reporting system is working again, the Investigator (or designate) must complete the SAE eCRF pages within 24 hours. The final valid information for regulatory reporting will be the information reported through the electronic SAE reporting system.

11.3.2 Follow-up and Final Reports

After the initial AE/SAE report, the Investigator is required to proactively follow each subject and provide further information on the subject’s condition to Atox Bio.

All SAEs documented at a previous visit/contact and designated as not recovered/not resolved or recovering/resolving will be reviewed at subsequent visits/contacts until the end of the study.

All AEs documented at a previous visit/contact and designated as not recovered/not resolved or recovering/resolving will be reviewed at subsequent visits/contacts until study end.

Follow-up information to an initial SAE report should be reported in the SAE eCRF pages within 3 business days. At the time of resolution of a SAE, a final report must be provided to the Sponsor by completing the appropriate SAE Report Form.

Any AE, regardless of severity, and whether or not ascribed to the IMP administration, will be recorded as such using medical terminology in the source documentation and on the appropriate eCRF pages. Whenever possible, diagnoses should be given when signs and symptoms are due to a common etiology (e.g. nausea and vomiting should be reported as "gastroenteritis" if gastroenteritis is the etiology of both). However, worsening sign(s) and symptom(s) of a diagnosis should be recorded separately. Patients withdrawn from the study due to AEs will be followed by the Investigator until the outcome is determined and, when appropriate, additional written reports and documentation will be provided.

All SAEs that have not resolved by the end of the study, or that have not resolved upon discontinuation of the patient's participation in the study, must be followed-up until either:

- the event resolves
- the event stabilizes
- the event returns to baseline, if a baseline value is available
- the event can be attributed to agents other than the study drug, or
- the event can be attributed to factors unrelated to study conduct

11.4 Disease Related Adverse Events

It is recognized that the patient population with abdominal sepsis or NSTI who require critical care support will experience a number of common aberrations in laboratory values, signs, and symptoms due to the severity of the underlying disease and the impact of standard therapies. These will not necessarily constitute an AE unless they require significant intervention, lead to discontinuation of blinded study medication, felt to be related to blinded study medication or are considered to be of concern, in the Investigator's clinical judgment. Examples of the type of AEs that may be associated with the abdominal infection, NSTI and sepsis are listed below.

11.4.1 List of Adverse Events that may be Associated with Abdominal Infection, NSTI, and Sepsis

Acute respiratory failure; respiratory distress; acute lung injury; acute respiratory distress syndrome (ARDS); acute renal failure; coagulation dysfunction; decreased platelets count; neutropenia; hypothermia; fever, bacteremia; sepsis, septic shock; hypotension; metabolic acidosis, pleural effusion; abdominal compartment syndrome; repeated surgeries/debridement; amputation.

For purposes of this study, deaths will be captured as clinical outcomes and do not need to be reported as SAEs unless felt related to study drug administration.

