5.2 Secondary Objectives

- To compare the rates of the primary endpoint at Day 14 between the Reltecimod- and placebo-treated patients.
- To compare time to the primary endpoint between the Reltecimod- and placebo-treated patients
- To compare AKI-free days over 14 and 28 days between the Reltecimod- and placebo-treated patients
- To compare the resolution of organ dysfunction (organ resolution is defined as having a SOFA score of ≤ 1 at Day 14, for individual organs and for total SOFA

score) between the Reltecimod- and placebo-treated patients over time and at Day 14

- To evaluate the effect of Reltecimod (compared to placebo-treated patients) in relation to the critical care and hospital stay parameters in patients with sepsis and AKI
 - Hospital length of stay
 - ICU length of stay
 - ICU free days in 28 days
 - Ventilator days
 - Ventilator free days in 28 days
 - Vasopressor days
 - Vasopressor free days in 28 days
 - RRT free days (days alive and free of RRT) in 28 days
- To compare survival status at Days 14 and 28 between the Reltecimod- and placebo-treated patients
- To tabulate the incidence of Stages 1, 2 and 3 AKI (using the KDIGO criteria) in patients with abdominal sepsis or NSTI
- To demonstrate the safety of Reltecimod in regard to susceptibility to secondary infections

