The safety profiles will be compared between active and placebo groups using descriptive statistics as appropriate for continuous and categorical safety variables. Changes in continuous safety measures such as laboratory values will be summarized by mean changes over time using descriptive statistics (sample size (N), mean, SD, median, minimum and maximum). The presence of clinically significant safety findings will be summarized by shift tables separately for each group using counts and percentages. AEs will be classified according to system organ class and preferred term and summarized by counts and percentages separately for those recorded on Day 0 (prior to drug administration) and those with onset on Day 1 or later. AEs will also be summarized by relationship to study drug, severity, and whether they are serious. Specific summaries will involve AEs and SAEs in the Infection/Infestation system organ class. Vital signs including weight, temperature, systolic BP, diastolic BP, respiration rate, and heart rate will be summarized across time (Day 0, Day 1, Day 2, Day 3, Day 7, Day 10, Day 14, Day 21 and Day 29) and separately by treatment group by N, Mean, and SD.

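### Protocol 11.2 and 11.4 give different rules for disease-related events, and the SAP has no analysis that isolates secondary infections, a stated safety objective

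*Protocol*

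**What the plan says.** **Objective.** Protocol 5.2 includes this secondary objective: "To demonstrate the safety of Reltecimod in regard to susceptibility to secondary infections". Protocol 11.1 also names secondary infections among the safety measures.

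**Reporting rule in 11.2.** "Worsening signs and symptoms of the underlying disease will be reported as AEs". The sentence has no condition attached. The same section says that potential secondary infections will be specifically captured. In the Section 7.3 visit schedule, the AE collection item names secondary infections at Day 3, Days 4 to 6, and Visits 5 to 9.

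**Reporting rule in 11.4.** This section concerns "common aberrations in laboratory values, signs, and symptoms due to the severity of the underlying disease and the impact of standard therapies". Of these it says: "These will not necessarily constitute an AE unless they require significant intervention, lead to discontinuation of blinded study medication". Two more exceptions follow: events "felt to be related to blinded study medication or are considered to be of concern" in the investigator's judgment. The examples in 11.4.1 include "neutropenia; hypothermia; fever, bacteremia; sepsis, septic shock; hypotension; metabolic acidosis".

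**Planned analysis.** SAP Section 6 says: "Specific summaries will involve AEs and SAEs in the Infection/Infestation system organ class". SAP 4.5 lists AEs among the safety endpoints but does not mention secondary infection. Appendix 1 lists AE Tables 14.3.1.1 to 14.3.1.11, and none is specific to infection.

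**The concern.** The study drug modulates T-cell co-stimulation, so whether it raises the risk of new infection is a natural safety question, and the protocol makes it an objective. AE records are the main data for it. Two sections of the protocol tell sites different things about overlapping events, and one of them lists infection diagnoses as examples of what need not be an AE. With up to 90 sites planned, a difference in reading becomes a difference in data.

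The planned output has a second weakness. Every enrolled patient has, or is suspected of having, a serious infection at entry. A class-level infection total therefore counts worsening of that infection together with anything new. If events are missed at the same rate in both arms, or diluted by index-infection events common to both, the absolute difference between arms shrinks. For an objective worded as demonstrating safety, that is the direction of false reassurance.

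**Working it through.** The documents give no rate of secondary infection and no reporting fraction, so the main check is a comparison of texts.

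**Step 1. Do 11.2 and 11.4 conflict?**

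| Question | Protocol 11.2 | Protocol 11.4 |
|---|---|---|
| Deterioration due to the index disease | AE, no condition | AE only if an exception applies |
| Who decides | No discretion | Largely the investigator |
| New infection after dosing | To be captured specifically | Not mentioned |

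They conflict on the first row. Protocol 11.3.2 sides with 11.2, since it asks for worsening features of a diagnosis to be recorded separately.

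**Step 2. How wide is the 11.4 exemption?** It is limited by cause to the underlying disease and standard treatment, and it has four exceptions. Discontinuation of study medication can hardly arise with a single 10-minute infusion. The other three (significant intervention, suspected drug relation, investigator concern) are real but undefined. The 11.4.1 examples go beyond laboratory values, signs and symptoms to infection diagnoses, with no limit by onset, organism or site. The exposed events are therefore non-serious new infections that a site attributes to the index illness.

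**Step 3. What separates new from index infection in the data?** Neither document defines a secondary infection. The patient listings in SAP Appendix 3 name no form for it. Protocol 8.1.6.1 and 9.2.5 and SAP 3.4 require the reason for each antimicrobial, distinguishing primary from secondary infection, and Listing 16.2.8.44 covers that form. However, Tables 14.1.4.2 and 14.1.4.5 summarize antimicrobials by category and drug, not by reason.

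**Step 4. What do the planned tables show?** Table 14.3.1.2 gives all treatment-emergent AEs by class and preferred term, so an infection row by arm will exist. Appendix 1 titles Table 14.3.1.5 as serious events by class, but SAP 9.1.2 describes the same number as serious drug-related events. No listed table separates new infection from index infection.

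**Step 5. Illustration, on assumed rates only.** Assume true secondary-infection rates of 30% (active) and 20% (placebo), 60 patients per arm, and the same reporting fraction s in both arms. Expected counts are 60 × 0.30 × s and 60 × 0.20 × s. The last column is the probability that the active count is no larger than the placebo count, from two independent binomials.

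| s | Active | Placebo | Difference | P(no excess seen) |
|---|---|---|---|---|
| 100% | 18.0 | 12.0 | 10 points | 0.121 |
| 80% | 14.4 | 9.6 | 8 points | 0.161 |
| 60% | 10.8 | 7.2 | 6 points | 0.212 |
| 40% | 7.2 | 4.8 | 4 points | 0.281 |

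Mixing can be shown in the same way. Suppose a fraction b of patients in each arm also has an index-infection event in the class, independently. The rates become 1 − 0.70(1 − b) and 1 − 0.80(1 − b), and the difference becomes 10(1 − b) points. With b = 20% the rates are 44% and 36%, a difference of 8 points, with P(no excess seen) = 0.21. With b = 60% they are 72% and 68%, a difference of 4 points, with probability 0.35.

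**The case against.** The strongest reply is that the protocol protects these events by several other routes, and most of that reply stands.

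- **Seriousness.** Protocol 11.3 requires every serious AE to be recorded, with no disease-related exemption for non-fatal events. New sepsis or septic shock would ordinarily need significant intervention, which restores AE status under 11.4 itself.
- **Explicit capture.** Protocol 11.2 and the visit items from Day 3 ask for secondary infections. A reader might infer that 11.4 hides them. The documents do not support that: the exemption is limited by cause, and capture is required elsewhere.
- **A second data source.** The antimicrobial record carries primary or secondary infection as the reason for use. A reader might infer that the objective cannot be answered. That is also too strong, because much of the needed data is collected but not tabulated. The source is incomplete, though: a new infection already covered by ongoing antibiotics may leave no new entry.
- **Neutropenia.** A reader might add it to the list of lost events because 11.4.1 names it. It does not belong there. Blood counts with differential are scheduled and reported in Tables 14.3.3.1 to 14.3.3.4, and Protocol 11.1.3 separately limits AE reporting of laboratory changes.
- **Planned tables.** The SAP does commit to a class summary, Table 14.3.1.2 shows preferred terms by arm, and the iDMC receives all safety data by group. What is missing is a dedicated, numbered table.
- **Size.** The illustrative rates come from no document. Equal under-reporting lowers the risk difference but leaves the expected risk ratio at 1.5 (0.30/0.20). Even with full reporting there is a 12% chance of seeing no excess, which reflects the sample size.

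What remains is the conflict between 11.2 and 11.4, the missing definition, and a summary that pools new with index infection.

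**Conclusion.** The point holds as a conflict between two reporting rules and a gap in the analysis plan. Sites following 11.2 and sites following 11.4 can both be compliant and record different data. The events at risk are non-serious new infections attributed to the index illness. No planned output isolates secondary infection, although it is a stated objective and a listed safety measure.

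The size is unknown. Under the assumed 30% and 20% rates, reporting of 80% down to 40% would reduce a 10-point excess to 8 down to 4 points and raise the chance of seeing no excess from 12% to 16% to 28%. These figures show direction only, and they assume equal reporting in both arms. The primary efficacy endpoint is not affected. Severity: should-fix.

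**What to change.** **Protocol 11.2 and 11.4.** Reconcile the two sections. State that an infection after dosing with a new organism, at a new site, or with onset after initial improvement is outside the 11.4 exemption and is always entered as an AE. Use the same three criteria as the definition of secondary infection, and add a yes/no flag on the AE page so that the specific capture promised in 11.2 has a field.

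**SAP Section 6 and Appendix 1.** Add a numbered table, in the As Treated set, of patients with at least one flagged secondary infection by arm, with the risk difference and its confidence interval. Cross-check the flag against antimicrobials whose recorded reason is secondary infection, and list the mismatches. Give the class summary a table number and align the two descriptions of Table 14.3.1.5. Include the new table in the iDMC package.

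**Cost.** One reconciling paragraph, one eCRF field and one table, with slightly more AE entry at sites. The antimicrobial reason is already collected. The flag should be introduced early, because AE detail that was not recorded at the time may not be recoverable.

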11.5 Safety Monitoring

The study medical monitor will assess all SAEs on an ongoing basis. Attention will be given to SAEs assessed as drug-related. The medical monitor may request unblinding of the treatment allocation of a patient for regulatory reporting purposes. The medical monitor will convene the independent data monitoring committee (iDMC) on ad-hoc basis if safety concerns arise from the medical monitor review.

11.6 Independent Data Monitoring Committee (iDMC)

An iDMC will be established to evaluate the safety of the study. An iDMC review of the safety data is planned after 60 patients (and possibly a second review depending on sample size re-estimation) have completed 28 days of the study.

For each planned iDMC review, all safety data on all patients who received one dose of Reltecimod will be made available to the iDMC. The data reviewed by the iDMC will be unblinded and presented by group to facilitate recommendations to the Sponsor. Data submitted to the iDMC review may be unaudited. A designated unblinded statistician will provide unblinded safety data to the iDMC using programs constructed and validated by the blinded Study Statistician and Statistical Programming Team. Further details on data management will be provided in the statistical analysis plan (SAP).

The iDMC may also meet on an ad-hoc basis when immediate safety concerns arise. In case of urgency, the chair of the committee could address any questions or concerns regarding the safety of the patients.

12. STATISTICS

12.1 Primary Effectiveness Endpoint

The primary effectiveness endpoint for this study is:

- Rates of achieving the primary endpoint of freedom from durable loss of renal function (defined as alive, free of dialysis, and less than a 37% loss of eGFR; (measured with the MDRD formula from the patient's reference eGFR)) at Day 28.

12.2 Secondary Effectiveness Endpoints

The secondary effectiveness endpoints for this study:

- Rates of the primary endpoint at Day 14 between the Reltecimod- and placebo-treated patients.
- To compare time to the primary endpoint between the Reltecimod- and placebo-treated patients over 14 days
- AKI-free days over 28 days
- Time to the primary endpoint
- Resolution of organ dysfunction (organ resolution is defined as having a total SOFA score of ≤ 1) at Day 14

- Resolution of specific organ dysfunction defined as having an individual organ SOFA score of ≤ 1 at Day 14
- Critical care and hospital stay parameters
 - Hospital length of stay
 - ICU length of stay
 - ICU-free days in 28 days
 - Ventilator days
 - Ventilator free days in 28 days
 - Vasopressor days
 - Vasopressor free days in 28 days
 - RRT free days (days alive and free of RRT) in 28 days
- Patient survival at Days 14 and 28
- Presence of Stages 1, 2 or 3 AKI (using the KDIGO criteria) in patients with abdominal sepsis or NSTI

12.3 Exploratory Measures

- Rates of improvement in durable loss of renal function (defined as alive, free of dialysis and improvement leading to a lower AKI stage but no better than Stage 1 AKI) at Days 14, 28 and 90
- AKD stages (AKD 0, 1, 2, 3 and 3F) at Days 14 and 28
- Incidence of CKD at Day 90
- Survival at Day 90
- Primary endpoint by baseline pathogen
- Evaluation of RRT use (i.e., type of RRT)
- Plasma and urinary biomarkers in patients with AKI
- To conduct an exploratory evaluation of blood leukocyte transcriptome (RNA expression) profiling in patients with SA-AKI and compare genomic profile in patients treated with Reltecimod versus placebo
- To define potential surrogate biomarkers (systemic) that exhibit change from baseline due to treatment with Reltecimod

